### 6.2.2 Study endpoint

The primary endpoint of the study is time to treatment failure, defined as

- Time to treatment failure where **treatment failure** is defined as:

a/ In the medical arm:

**Need for treatment other than esomeprazole for control of symptoms of reflux disease:**

In order to allow for a stringent assessment of treatment failure ask the following question:

*“Do you have sufficient control of your heartburn and acid regurgitation?”*

If the answer is **No**, continue with:

*“Do you need other regular drug treatment to control your symptoms?”*

If the answer to this question is **Yes** and the dose of esomeprazole is 20 mg once daily, then the dose is to be increased to 40 mg once daily. The subject will be treated with the increased dosage for 8 weeks before a second dose adjustment can be made.

If the answer to this question is **Yes** and the dose is esomeprazole 40 mg once daily, then the dose is to be changed to 20 mg twice daily. The subject will be treated with the changed dosage for 8 weeks before being classified as a treatment failure if sufficient symptom control has not been achieved.

If the answer to this question is **Yes** and the dose is 20 mg twice daily, then the subject is a **treatment failure and will be withdrawn**.

b/ In the surgical arm:

**Need for medical treatment for control of symptoms from reflux disease:**

In order to allow for a stringent assessment of treatment failure ask the following question:

*“Do you have sufficient control of your heartburn and acid regurgitation?”*

If the answer is **No**, continue with:

*“Do you need other regular drug treatment to control your symptoms?”*

If the answer to this question is **Yes**, the subject has to be classified as a **treatment failure and will be withdrawn**.

If the answer to this question is **Yes** and one dilatation has been done, then the subject is a **treatment failure and will be withdrawn**.

Furthermore the subject will also be regarded as a **treatment failure** if the following occurs;

- Post-operative - post-fundoplication complaints requiring further medical actions to control symptom burden
- Per-operative death
- Post-operative death within 30 days after surgery
- Dysphagia requiring further treatment. In case of esophageal stenosis, one dilatation is allowed.

### **6.2.3 Statistical analyses**

The two treatment groups will be compared regarding the primary endpoint using Life Table methods for graphic presentation and a log rank test (two-sided) for statistical inference. In both the ITT and the PP analyses data will be censored in case of discontinuation due to reasons other than treatment failure. Post-operative complications, histopathology, endoscopy and symptoms are summarized using frequency tables.

For subjects randomized to the surgery group, post-operative complications during the first month after surgery will be assessed descriptively. Quantitative data on post-operative complications will be tabulated with Mean, SD, min and max. For post-operative complications data with nominal or ordinal outcome, the number of subjects and relative frequency distribution will be presented.

Histopathological changes will be assessed by frequency tabulation by treatment group and visit.

The number of endoscopic and/or symptomatic relapses at clinical visits will be presented by visit and treatment group with frequency tables. Mean, SD, min and max, both combined and separately.

Number of endoscopic and/or symptomatic relapses between visits will be presented by time period (subject year) and treatment group with frequency tables. Mean, SD, min and max, both combined and separately.

GI symptoms associated with GERD over time will be presented by visit and treatment in frequency tables and as number and proportion of subjects with no symptoms.

The percentage of 24 hr intragastric pH  $\leq 4$  will be presented using descriptive methods (Mean, SD) by visit and treatment group.

Symptom Association Probability (SAP) will be presented using descriptive methods (Mean, SD) by visit and treatment group.

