### Study design

This study is designed as a 5-year, randomized, open, parallel-group multicentre trial with a 5-year prolongation. The objectives are to estimate the efficacy and tolerability of esomeprazole compared with laparoscopic anti-reflux surgery, in a long-term treatment of adult subjects with chronic gastroesophageal reflux disease (objectively documented by endoscopy and/or abnormal 24 hour pH metry (see Section 4.3.8.)). The study will begin with a 12-week run-in period allowing recording of baseline values and responses to medical treatment with esomeprazole. This period will end with a randomization between the two therapeutic strategies.

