**Table 3 Efficacy objectives and endpoints relating to each objective**

Objective	Endpoint(s)	Summary statistic for analysis (incl. timepoint and population)	Planned analysis	Significance of results
Primary				
4.1, 4.3.2 To compare treatments with regard to treatment failure	Number of days, treatment failure (yes/no)	Median number of days  ITT population	Logrank test, and survival curves	Longer time to treatment failure indicates a more efficient treatment
Other				
4.3.3 Histopathological findings	Histological assessments .	All histological presentations will be performed for the safety population and ITT population.	No formal statistical comparison	
4.3.4 Periodic prevalence of endoscopic and symptomatic recurrences	Endoscopic relapse (LA grade C-D) between scheduled endoscopies. Symptomatic relapse between scheduled visits	Mean number of relapses per time period (subject year). ITT population	Descriptive descriptive	
4.3.4 Point prevalence of endoscopic and symptomatic recurrences	Endoscopic relapse (LA C-D) at scheduled endoscopies. Symptomatic relapse at scheduled visits.	Mean number of relapses per scheduled endoscopy visit. ITT population		
4.3.5 GI symptoms assoc. with GERD over time	Symptom assessments at clinical visits	Proportion of subjects with no symptoms ITT population	descriptive	
4.3.6 Per-operative events	Per-operative event assessments during the operation	Proportion of subjects randomized to surgery with per-operative symptoms ITT population	descriptive	
4.3.7 Post-operative symptoms and events	Post-operative symptom assessments during the first 30 post-operative days	Proportion of subjects randomized to surgery with post-operative symptoms ITT population	descriptive	
4.3.8 24 hr intragastric and intraesophageal pH	% of time with intragastric and intraesophageal pH $\leq$ 4	ITT population	Descriptive	
4.3.8 Symptom Association Probability (SAP)	Association between symptoms and reflux episodes	ITT population	Descriptive	

The methods for collecting efficacy data are presented below.

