## **6. STATISTICAL METHODS AND DETERMINATION OF SAMPLE SIZE**

### **6.1 Determination of sample size**

The true rate of treatment successes (i.e. subjects who have not experienced treatment insufficiency within 5 years) is assumed to be at least 70% for both treatments. With 275 subjects on each treatment the true difference between treatment is, with a probability of 95%, not going to differ by more than 8 percentage points from the observed difference.

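### The trial is sized on the precision of the 5-year success difference, but the planned primary analysis never produces that difference or a confidence interval

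*Protocol*

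**What the plan says.** **Sizing (Protocol 6.1).** The quantity is the proportion of "subjects who have not experienced treatment insufficiency within 5 years", which "is assumed to be at least 70% for both treatments". I read insufficiency here as the treatment failure of Section 4.1. The justification is: "With 275 subjects on each treatment" the true difference is "with a probability of 95%, not going to differ by more than 8 percentage points from the observed difference". The section states no power, hazard ratio, margin or number of events.

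**Aim.** The synopsis says under study design: "The objectives are to estimate the efficacy and tolerability of esomeprazole compared with laparoscopic anti-reflux surgery". Section 3.1 repeats this. The primary objective in Section 2.1 is framed as assessing time to treatment failure.

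**Analysis.** Section 6.2.3 compares the arms "using Life Table methods for graphic presentation and a log rank test (two-sided) for statistical inference". Section 6.2.1 says the same without the sidedness, and the synopsis names the logrank test alone. For the primary objective, Table 3 lists "Median number of days" as the summary statistic in the ITT population, and a logrank test with survival curves as the analysis.

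**Looks.** Section 6.2.4 plans interim analyses at 3 and 5 years to evaluate efficacy and tolerability and names no estimator. Follow-up runs to 10 years.

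**The concern.** The sample size and the analysis answer different questions. Section 6.1 promises an estimate of a difference with known precision. The analysis sections promise a test and a median. A logrank test gives a p-value without an effect size, and the summary chosen beside it is one that a high success rate tends to leave undefined.

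At stake is whether the report contains the number for which 550 subjects were randomized. If the plan is followed as written, a reader could see two curves and a p-value but no planned statement of how far apart the strategies are at 5 years, or how uncertain that is. If the test were non-significant, nothing in the named output would show how large a difference remained compatible with the data.

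**Working it through.** **Inputs.** From Section 6.1: 275 per arm, success of at least 70% in each arm at 5 years, 95% confidence, 8 points. From the synopsis and Section 3.2: 10 years of follow-up. The protocol gives no significance level for the logrank, no dropout rate and no hazard shape. I assume two-sided 0.05 from the 95% level and a constant hazard unless stated otherwise.

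**Step 1: the plan's own figure.** Half-width = 1.96 × √(2 × p(1 − p)/n).
- At p = 0.70 and n = 275: 1.96 × √(2 × 0.70 × 0.30/275) = 0.0766, or 7.66 points. Adding a continuity correction of 1/275 gives 8.02 points. The stated 8 points reproduces.
- For exactly 8 points, n is 253 per arm without the correction and 277 with it.
- At 75%, 80% and 90% success the half-width is 7.2, 6.7 and 5.0 points, so 70% is the conservative end of the stated range.

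Section 6.1 is therefore a confidence-interval calculation for a difference in proportions.

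**Step 2: look for that quantity in the analysis.**

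| Place | Summary | Inference | 5-year difference or interval |
|---|---|---|---|
| Synopsis, statistical methods | none | logrank | no |
| Table 3 | median days | logrank, survival curves | no |
| 6.2.1 | life table, as a graph | logrank | no |
| 6.2.3 | life table, as a graph | two-sided logrank | no |
| 6.2.4 | none | none named | no |

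**Step 3: when is the median reached?**
- At 3 and 5 years: survival free of failure is at least 0.70, above 0.50, so the median is not reached whatever the hazard shape. If the earliest subjects carried about a year of extra follow-up at the 5-year look, S(6) = 0.70^(6/5) = 0.65 under constant hazard, still above 0.50.
- At 10 years under constant hazard: S(10) = S(5)² and median = 5 × ln 2/(−ln S(5)).

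| 5-year success | S(10) | Median (years) |
|---|---|---|
| 70% | 0.49 | 9.7 |
| 75% | 0.56 | 12.0 |
| 80% | 0.64 | 15.5 |
| 90% | 0.81 | 32.9 |

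The median passes 10 years once S(5) exceeds √0.5 = 0.707.
- Sensitivity at exactly 70% (Weibull): a falling hazard (shape 0.75) gives 12.1 years, a rising hazard (shape 1.25) gives 8.5 years.
- Simulated Kaplan-Meier curves, 275 per arm, constant hazard, with no dropout or 5% a year: at 70% the median was reached by 10 years in about 62–63% of arms, but its upper 95% limit in only about 6%. At 75% the median was reached in about 2–3% of arms, and at 80% in none.

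**Step 4: precision of the replacement estimate.** Without censoring, the Greenwood variance of the 5-year rate equals the binomial variance, so the half-width stays 7.66 points at 70%. If 10% or 20% of the information were lost (assumed), it would be 7.66/√0.9 = 8.1 or 7.66/√0.8 = 8.6 points.

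**Step 5: what the logrank can detect.** Power = Φ(|ln HR| × √events/2 − 1.96), with HR = ln p₂/ln p₁ and no loss.
- 70% v 78%: 143 events and 58% power at 5 years; 248 events and 81% at 10 years.
- 70% v 62%: 187 events and 52% at 5 years; 310 events and 73% at 10 years.
- 70% v 85%: 124 events and 99% at 5 years.

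**The case against.** The strongest defence is that the test fits the endpoint. The primary objective concerns time to treatment failure, Table 3 speaks of comparing the treatments, and a logrank test does that. The word estimate appears only in the design description. A full SAP is announced in Section 6.2.1 and is not shown; variance formulas, landmark times and interval output commonly sit there. This stands as a defence of the logrank. It does not defend the summary: the protocol does not leave that open but fixes the median in Table 3, and it gives the life table a graphic role only. A SAP that reported the 5-year difference as primary would have to add to or override the protocol.

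Three stronger readings are tempting, and the documents do not support them.
- A reader might infer that the plan yields nothing but a p-value and a median. Survival curves are planned, and each arm's 5-year success can be read from them. What is missing is the difference and its interval.
- A reader might infer that the median cannot be estimated in this trial at all. That is certain only for the 3- and 5-year analyses. At exactly 70% it falls just inside 10 years, and earlier with a rising hazard.
- A reader might infer that a non-significant logrank is the likely result. The 70% is a floor for both arms, not an assumption that they are alike; 70% v 85% satisfies it. The 52–58% power applies to the 5-year interim look, and 8 points is a precision target, never a difference to be detected.

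Nor does the protocol make any equivalence or non-inferiority claim.

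**Conclusion.** The point holds as a mismatch between the basis of the sample size and the stated primary summary. The sizing arithmetic is correct, the logrank is an acceptable test, and the number of subjects is adequate for the estimate that Section 6.1 describes. What fails is that no section delivers that estimate, and the summary fixed in its place is undefined at both interim analyses and borderline or unreached at the end.

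The 3- and 5-year part rests only on the protocol's own 70% floor. The 10-year part rests on an assumed constant hazard, with the Weibull range as its sensitivity. The half-widths assume no loss unless stated, since the protocol gives no dropout rate. The conclusion does not depend on what the trial's result turns out to be.

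**What to change.** In Table 3 and Section 6.2.3:
- Replace or supplement the median with the Kaplan-Meier or life-table success rate per arm at 5 years, and also at 3 and 10 years.
- Name the between-arm difference at 5 years, with a 95% confidence interval from the Greenwood variance, as the primary effect estimate.
- Keep the two-sided logrank as the accompanying test.
- If the median is kept, say that it is reported only where reached.

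Optional: add the 10-year precision to Section 6.1. At S(10) = 0.49 without loss it is 1.96 × √(2 × 0.49 × 0.51/275) = 8.4 points. A sentence saying that a non-significant logrank will not be read as similarity would do no harm but is not required.

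The cost is protocol and SAP wording and standard output. No new data, visits or subjects are needed.

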During the 5-year prolongation, all subjects will visit the hospital after 6, 7, 8, 9 and 10 years for assessments. At 5.5, 6.5, 7.5, 8.5 and 9.5 the subjects will have a telephone visit (hospital visit optional). The hospital visit should be done by the investigator and the telephone should preferably be done the investigator.

Randomized subjects who have discontinued but not withdrawn their informed consent will be followed-up by a phone call from the investigators at 5 and 10 years after randomization. This will also be applicable for subjects who discontinue during the prolonged period. The follow-up phone call consists of questions about the subject's surgery related to GERD, present medical treatment of GERD and present symptom load. For more information see Appendix P to the amendment

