### **3.3.5 Discontinuation of subjects from treatment or assessment**

#### **3.3.5.1 Criteria for discontinuation**

Subjects may be discontinued from study treatment and assessments at any time, at the discretion of the investigator(s). A subject may, however, continue the study under exceptional circumstances (e.g. if continuation of study treatment or follow-up actions are necessary for the subjects safety and well-being, and the continuation of the study is not expected to be associated with any risk or discomfort for the subject). Specific reasons for discontinuing a subject from this study are:

1. Withdrawal of informed consent
2. Unwillingness to continue the study or lost to follow-up.
3. Any unacceptable adverse event, including laboratory result or physical findings, as judged by the investigator
4. Any “alarm symptoms” which, in the investigator’s judgement, requires treatment outside this protocol.
5. Continuous need for/intake of drugs listed under Section [3.3.4](#) criteria 7.
6. Protocol non-compliance as judged by the investigator
7. Classified as treatment failure
8. Pregnancy
9. Incorrect enrolment or randomization of subject
10. Other reason specified by the investigator.

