**Need for treatment other than esomeprazole for control of symptoms of reflux disease:**

In order to allow for a stringent assessment of treatment failure ask the following the question:

*“Do you have sufficient control of your heartburn and acid regurgitation?”*

If the answer is **No**, continue with:

*“Do you need other regular drug treatment to control your symptoms?”*

If the answer to this question is **Yes** and the dose of esomeprazole is 20 mg once daily, then the dose is to be increased to 40 mg once daily. The subject will be treated with the increased dosage for 8 weeks before a second dose adjustment can be made.

If the answer to this question is **Yes** and the dose is esomeprazole 40 mg once daily, then the dose is to be changed to 20 mg twice daily. The subject will be treated with the changed dosage for 8 weeks before being classified as a treatment failure if sufficient symptom control has not been achieved.

If the answer to this question is **Yes** and the dose is 20 mg twice daily, then the subject is a **treatment failure and will be withdrawn.**

b/ In the surgical arm:

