**Need for medical treatment for control of symptoms from reflux disease:**

In order to allow for a stringent assessment of treatment failure ask the following question:

*“Do you have sufficient control of your heartburn and acid regurgitation?”*

If the answer is **No**, continue with:

*”Do you need other regular drug treatment to control your symptoms?”*

If the answer to this question is **Yes** the subject has to be classified as a **treatment failure and will be withdrawn**.

Furthermore, the subject will also be regarded as a **treatment failure** if the following occurs;

- Post-operative - post-fundoplication complaints requiring further medical actions to control symptom burden.
- Per-operative death
- Post-operative death within 30 days after surgery
- Dysphagia requiring further treatment. In case of esophageal stenosis, one dilatation is allowed.

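### The primary endpoint is not parallel between arms: listed surgical harms count as treatment failure, while esomeprazole withdrawals for adverse events are censored and anti-reflux surgery is not clearly classified

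*Protocol*

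**What the plan says.** **Censoring.** Protocol Section 6.2.3 compares the arms with a "log rank test (two-sided) for statistical inference" and fixes one rule for both analysis populations, ITT and PP: "data will be censored in case of discontinuation due to reasons other than treatment failure".

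**Failure in the surgical arm** (Sections 4.1 and 6.2.2). Need for regular drug treatment to control reflux is a failure. So are listed consequences of the operation: "Post-operative - post-fundoplication complaints requiring further medical actions to control symptom burden", dysphagia that needs further treatment (one dilatation for stenosis is permitted), death during surgery, and death within 30 days after it.

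**Failure in the medical arm** (same sections). The heading is "Need for treatment other than esomeprazole for control of symptoms of reflux disease". The operative question is "Do you need other regular drug treatment to control your symptoms", and failure is reached only at the end of the dose-adjustment steps. There is no tolerability or death component.

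**Discontinuation reasons** (Section 3.3.5.1). Reason 3 is "Any unacceptable adverse event, including laboratory result or physical findings, as judged by the investigator". Reason 2 covers unwillingness to continue and loss to follow-up. Classification as treatment failure is a separate entry, reason 7.

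**Follow-up after discontinuation** (Section 3.1). Subjects who stopped without withdrawing consent "will be followed-up by a phone call from the investigators at 5 and 10 years after randomization". The call covers GERD surgery, current GERD medication and symptom load. Section 6.2 gives these answers no role.

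**The concern.** A logrank comparison is interpretable when the event means the same thing in both arms. Here a surgical subject who is harmed in one of the listed ways has an event. A medical subject who stops because of an adverse effect of the drug leaves the risk set without one. Table 3 nevertheless reads a longer time to failure as showing the more efficient treatment, and the primary objective in Section 2.1 is control of reflux disease. Part of any observed difference could come from the definition rather than from reflux control.

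In a drug-versus-surgery trial, a subject who moves from the drug to an operation is a central outcome. The medical-arm heading is broad enough to include surgery for uncontrolled reflux, but the question beneath it asks only about drugs. The surgical arm has a gap of its own: re-operation for recurrent reflux without regular drug treatment is not named.

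Because ITT and PP share the censoring rule, the PP analysis cannot serve as a check on it.

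**Working it through.** **Step 1. How the stated rules classify each situation**

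| Situation | Medical arm | Surgical arm |
|---|---|---|
| Reflux uncontrolled, regular drugs needed | Failure, after dose escalation | Failure |
| Listed procedural harm (complaints, dysphagia, peri-operative death) | No counterpart | Failure |
| Withdrawal for an unacceptable adverse event outside the failure list | Censored | Censored |
| Unwillingness unrelated to symptom control | Censored | Censored |
| Anti-reflux surgery or re-operation for reflux, no regular drugs | Ambiguous: heading and question differ | Not named |

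Row 2 creates the asymmetry: the main treatment-specific harms are events in the surgical arm, while the medical arm's harms fall into row 3.

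**Step 2. The protocol's own precision figure** (Section 6.1: 275 per arm, 70% success, 95%)

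Half-width = 1.96 × √(2 × 0.70 × 0.30 / 275) = 7.66 points. With a continuity correction of 1/275 it is 8.02 points. The stated 8 points is reproduced and this issue does not affect it.

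**Step 3. Illustration of the effect of the rule**

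Assumptions, none of them from the protocol except the 70%:
- Constant hazards, with reflux failure giving 70% success at 5 years in both arms.
- A treatment-burden event (side effect or intolerance) that affects x% by 5 years in both arms, independently of reflux failure.
- All of this burden falls under the listed failures in the surgical arm and is censored in the medical arm.

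Formulas at 5 years:
- Medical arm, Kaplan-Meier success under the rule: 0.70.
- Surgical arm: 0.70 × (1 − x).
- Hazard ratio, medical to surgical: ln 0.70 / [ln 0.70 + ln(1 − x)].
- Chance of a significant result favouring esomeprazole: Φ(|ln HR| × √D / 2 − 1.96), where D is the total number of events. Two-sided 0.05 is assumed, because the protocol states no level.

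| x | Medical | Surgical | Gap (points) | HR | Events, S + M | Chance |
|---|---|---|---|---|---|---|
| 2% | 70.0% | 68.6% | 1.4 | 0.95 | 86 + 82 | 5% |
| 5% | 70.0% | 66.5% | 3.5 | 0.87 | 92 + 81 | 14% |
| 10% | 70.0% | 63.0% | 7.0 | 0.77 | 102 + 79 | 41% |

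If the same kinds of event counted in both arms, both would stand at 0.70 × (1 − x). The gap would be 0, the HR 1, and the chance in that direction 2.5%.

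**Step 4. What drives the gap**

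Let the burdens differ, x_M in the medical arm and x_S in the surgical arm. Under the rule the difference is 0.70 − 0.70(1 − x_S). With parallel counting it is 0.70(1 − x_M) − 0.70(1 − x_S). The rule therefore shifts the difference by 0.70 × x_M. For x_M of 2, 5 and 10% that is 1.4, 3.5 and 7.0 points, whatever the surgical burden. The unknown quantity is how many medical-arm subjects leave for reasons related to their treatment.

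**The case against.** The strongest reply is that this is partly a choice of endpoint. The objective is reflux control, and adverse events leading to discontinuation are reported separately and descriptively (Table 4 and the safety analyses), so these withdrawals stay visible. That explains leaving tolerability out of the medical arm. It does not explain putting procedural harm into the surgical arm of the same endpoint.

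Other objections stand, and they rule out stronger readings that a reader might infer:

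- **That a switch to surgery is always censored.** The medical-arm heading is not limited to drugs, so surgery for uncontrolled reflux may well be a failure. The text is ambiguous.
- **That all dissatisfaction is censored.** Dissatisfaction from poor reflux control is what the first failure question asks about, and Section 3.1 sends subjects with recurrent symptoms through it. Only dissatisfaction for other reasons is clearly censored.
- **That every harm of surgery is a failure.** Only the listed ones are. Bleeding, perforation, infection and similar complications are tabulated descriptively, and surgical-arm withdrawals for other reasons are censored as well.
- **That every gap favours esomeprazole.** Leaving re-operation for recurrent reflux unnamed would favour surgery.
- **That the Kaplan-Meier and logrank results are shown to be biased.** If departures are independent of reflux failure, both remain valid for the failure as defined. The gap in Step 3 lies between two endpoint definitions. Informative censoring is possible, more so in an open study, but the protocol contains nothing that demonstrates or measures it.
- **That no analysis will address this.** Section 6.2.1 promises a statistical analysis plan, which is not at hand and may add sensitivity analyses. Only the protocol's silence can be stated.

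Finally, the 12-week run-in on esomeprazole, with response required before randomization, should remove some early intolerance. That makes the larger values of x less likely, without fixing a figure.

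**Conclusion.** The point holds in a limited form. As written, the primary endpoint combines reflux control with listed treatment harms in the surgical arm and covers reflux control alone in the medical arm. The censoring rule in Section 6.2.3 carries that difference into both ITT and PP. Anti-reflux surgery in the medical arm is left ambiguous, and re-operation for recurrent reflux in the surgical arm is not named.

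The size cannot be derived from the protocol. Under the stated assumptions the rule shifts the 5-year difference towards esomeprazole by 0.70 × x_M: about 1.4 points at 2% and 7.0 at 10%, the latter close to the 8-point precision. The shift is negligible if few medical-arm subjects leave for treatment-related reasons.

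This does not invalidate the primary analysis or the sample-size figure. It should be corrected because it affects how the primary result can be read and the remedy is cheap.

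**What to change.** Keep the primary definition and make two additions.

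1. **Sections 4.1 and 6.2.2, and the synopsis.** Reconcile the medical-arm heading with the question beneath it, so that the endpoint states how anti-reflux surgery in the medical arm is classified. State likewise how re-operation in the surgical arm is classified.
2. **Section 6.2.3.** Pre-specify a sensitivity analysis, reported beside the primary one, with the same components in both arms. Discontinuation for an adverse event or for treatment-related dissatisfaction, and any anti-reflux surgery or re-operation, would count as failure on the date it occurs. For discontinued subjects, use the answers from the 5- and 10-year calls. For those still censored, report a bound under worst-case assumptions.

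Cost: protocol wording and extra analysis, with no new visits, since discontinuation reasons and the call answers are already to be collected. The calls give status only at two time points, so some event dates will be approximate. The medical-arm success rate may look less favourable in the added analysis.
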